## 9.4 STATISTICAL ANALYSES

### 9.4.1 GENERAL APPROACH

Continuous measures will be described using means and standard deviations (or medians and ranges if non-normality is detected), while categorical measures will be summarized with frequencies and percentages.

For inferential tests, a two group t-test will be used to look for trends in the data.

Analyses for primary and secondary endpoints are described individually, below.

The distribution of the data will be examined to ensure that parametric testing is appropriate. In cases where data distributions are not normal, nonparametric tests will be used to analyze the data.

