## 3 OBJECTIVES AND ENDPOINTS

Objectives	Endpoints
Primary	
Primary Endpoint: Feasibility and Acceptability as measured by the responses on the individual items on the feasibility and acceptability questionnaire
 
Secondary Endpoint: Attrition as measured by the percent of participants completing the study
 
Secondary Endpoint: Adherence as measured by the percentage of missing data over the course of the study

To establish feasibility and acceptability of our intensive data collection protocol.	
Exploratory	
Change from baseline in self-reported strain as measured by Care-QOL Strain at the end of the 3-month (90 day) intervention period
 
Change from baseline in self-reported depression as measured by PROMIS Depression at the end of the 3-month (90 day) intervention period
 
Change from baseline in self-reported anxiety as measured by PROMIS Anxiety at the end of the 3-month (90 day) intervention period

Examine the impact that the JITAI has on improving self-reported mental health (caregiver strain, depression and anxiety) in care partners.	

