#### Exploratory Endpoints:

- 1) We hypothesize decreases from baseline to 3-months in caregiver strain among participants in the JITAI group.
- 2) We hypothesize decreases from baseline to 3-months in depression among participants in the JITAI group.
- 3) We hypothesize decreases from baseline to 3-months in anxiety among participants in the JITAI group.

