## 9.2 SAMPLE SIZE DETERMINATION

The main purpose of the current trial is to establish the feasibility and acceptability of an intensive data collection protocol in order to inform the a larger, later-stage effectiveness study on the JITAI in care partners of persons with chronic medical conditions. Thus, the current study is designed to provide a point of estimate for the effect of the JITAI for this future large-scale trial. Given that there are no formal power analysis calculations for this type of analysis, we have based the proposed sample size on our previous experience conducting these types of trials. Specifically, we believe that ~50 participants will provide sufficient numbers and diagnostic diversity to evaluate feasibility and acceptability of new mobile health apps. Thus, or sample size of N=60 caregivers (30 per arm and 20 per care partner group), exceeds this estimate and should provide a reasonable range of scores on the HRQOL outcome measures to guide later phase trial work.

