## 9.3 POPULATIONS FOR ANALYSES

The primary endpoint will examine survey responses on the feasibility and acceptability questionnaire that is designed to evaluate our intensive data collection protocol in the full sample (i.e., N=60 care partners). Secondary endpoints will include attrition and adherence estimates (again across the full sample). Exploratory analyses will be conducted to identify trends for an improvement in HRQOL scores (i.e., strain, depression, and anxiety) for care partners that are randomized to the intervention group. These analyses will also look for a trend for an improvement in the remaining HRQOL scores for care partners that are randomized to the intervention group, and will compare the JITAI group with the control group on all of the different HRQOL measures. Exploratory analyses may also compare important subgroups (e.g., caregiver groups that differ by diagnosis [SCI, HD or HCT], relationship type [parent vs. spousal caregivers], caregiver groups that differ by sex [male vs. female caregivers], caregiver groups that differ according to the functional status of the person with TBI (e.g., complicated mild vs. moderate vs. severe TBI or perceived functional status based on Mayo Portland Adaptability Index scores). Exploratory analyses will be an intention-to-treat approach where the participant will contribute data to the arm he/she was randomized to regardless of the amount of data contributed (i.e. the duration of participation).

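### The exploratory hypotheses are worded as falls within the JITAI arm, and the only follow-up test named, a two-group t-test, adjusts for neither baseline nor condition

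*Combined protocol and SAP*

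**What the plan says.** - **Hypotheses (9.1, Exploratory Endpoints).** For strain: "We hypothesize decreases from baseline to 3-months in caregiver strain among participants in the JITAI group". The depression and anxiety hypotheses have the same form. Control is not mentioned.
- **Endpoint (section 3).** "Change from baseline in self-reported strain as measured by Care-QOL Strain at the end of the 3-month (90 day) intervention period", and likewise for PROMIS Depression and Anxiety. The objective above these endpoints concerns the impact of the JITAI.
- **Comparison (9.3).** The exploratory analyses look for improvement in the intervention group and also "will compare the JITAI group with the control group on all of the different HRQOL measures".
- **Purpose (9.2).** "the current study is designed to provide a point of estimate for the effect of the JITAI for this future large-scale trial".
- **Method (9.4.1).** "For inferential tests, a two group t-test will be used to look for trends in the data", then "In cases where data distributions are not normal, nonparametric tests will be used to analyze the data". Sections 9.4.2 and 9.4.3 cover only the primary and secondary endpoints. The tests in 9.4.4 are for baseline differences.
- **Condition.** Section 4.1 gives SCI, HD and HCT a separate randomisation list each. In 9.3, condition enters the exploratory analyses only as an option: "Exploratory analyses may also compare important subgroups".
- **Baseline timing.** Sections 4.1 and 8.1.2 place randomisation before baseline data collection.

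**The concern.** The hypotheses and the purpose do not match. Scores in both arms may fall for reasons unrelated to the JITAI. Section 2.3.2 says that wearing the Fitbit may itself help, and under 6.1 both arms wear it and can open the same dashboard. A fall in the JITAI arm alone would then meet the 9.1 wording and could be reported as support for the intervention.

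The named test also leaves precision unused. Baseline scores and condition are collected on everyone, but a two-group t-test uses baseline at most by subtraction and ignores condition. Section 9.2 wants an estimate of the JITAI effect for a larger trial, so the width of its interval matters even in a feasibility study.

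**Working it through.** **Hypothesis wording.** Sections 3, 4.1, 9.2 and 9.3 ask whether JITAI differs from control. Section 9.1 asks whether JITAI participants fall. If both arms fall by the same amount, the answers are no to the first and yes to the second. No arithmetic is needed.

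**Precision.** The plan gives no power or precision figure to reproduce; 9.2 rests on previous experience. Its arithmetic is consistent: 2 × 30 = 3 × 20 = 60.

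Inputs:
- n = 30 per arm (9.2).
- SD = 10, the T-metric reference SD in 8.1.5, assumed to hold in this sample at both times.
- Baseline to Day-90 correlation ρ: not in the documents; range 0.5 to 0.8 assumed.

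Formulas:
- Variance of change: 2(1 − ρ) × SD².
- ANCOVA residual variance: (1 − ρ²) × SD².
- Ratio of change score to ANCOVA: 2(1 − ρ)/(1 − ρ²) = 2/(1 + ρ).
- 95% CI half-width: t × (residual SD) × √(2/n), with t = 2.002 on 58 df (t-test) or 57 df (ANCOVA), and √(2/30) = 0.2582.

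| ρ | Variance ratio | t-test on change | ANCOVA |
|---|---|---|---|
| 0.5 | 1.33 | 5.17 | 4.48 |
| 0.6 | 1.25 | 4.62 | 4.14 |
| 0.7 | 1.18 | 4.00 | 3.69 |
| 0.8 | 1.11 | 3.27 | 3.10 |

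At ρ = 0.5, for example: 2.002 × 10.00 × 0.2582 = 5.17 against 2.002 × 8.66 × 0.2582 = 4.48. Chance baseline imbalance multiplies the ANCOVA half-width by about √(1 + 1/56) = 1.009, giving 4.52 at ρ = 0.5 and 3.13 at ρ = 0.8. ANCOVA with 30 per arm is worth 30/0.90 = 33 to 30/0.75 = 40 per arm unadjusted. A t-test on the Day-90 score alone has half-width 5.17 at every ρ.

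**Condition.** The documents give no between-condition variance. If condition explains 0, 5 or 10% of the residual variance, the half-width changes by about 0, −2.5% (√0.95 = 0.975) or −5% (√0.90 = 0.949).

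**Day 30 and 60 scores.** A simulation with 30 per arm, 20% random dropout and equal correlation between visits (8,000 runs per ρ) gave a repeated-measures model 2 to 3% less variance than ANCOVA in completers. With correlation decaying over time, it was 5 to 6% less.

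**Baseline after randomisation.** Suppose reported baseline shifts by d in one arm and the shift does not persist to Day 90. The change-score estimate moves by d, the ANCOVA estimate by ρ × d (equal SDs), and the unadjusted Day-90 difference by 0. For d = 1 T-point (illustrative) these are 1.0, 0.5 to 0.8, and 0.

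**The case against.** The case for leaving the plan alone is reasonable. These are exploratory outcomes in a feasibility trial. A two-group comparison of randomised arms is valid, 9.3 already plans it, and 9.2 sets no precision target. The gain from adjustment is 0.17 to 0.69 T-points of half-width (3.27 − 3.10; 5.17 − 4.48) and depends on an assumed correlation. All of this stands and limits the weight of the point. It does not reconcile 9.1 with 9.3, or supply the unstated test variable.

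Several stronger readings are tempting but not supported:

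- **That a within-arm test will be used to claim efficacy.** No such test is named. With 30 JITAI participants and the same assumptions, a paired t-test would call a shared fall of 2 to 4 T-points significant in 18 to 92% of trials. Nobody plans that test, so this is not the size of the problem.
- **That dropping people without a Day-90 score breaks intention-to-treat.** Section 9.3 includes participants "regardless of the amount of data contributed (i.e. the duration of participation", but in context this reads as a rule about which arm they are counted in. What is missing is a statement of how absent Day-90 scores are handled. No dropout bias is shown.
- **That 20% attrition leaves 24 per arm.** Section 7.1 replaces participants who withdraw or are discontinued, and sections 1.1 and 4.1 allow 60 to 90 enrolled. With 90 enrolled, a 20% loss leaves 36 per arm. The 24-per-arm case (half-width 5.81 against 5.04 at ρ = 0.5) is a no-replacement worst case.
- **That the plan never checks baseline balance.** Section 9.4.4 compares baseline HRQOL between arms. It states no action if they differ. Section 6.2 has only the JITAI group told about the prompts at the baseline visit, but no section says this precedes the HRQOL survey, so a shift is possible rather than shown.

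**Conclusion.** The point holds as an almost free improvement to the exploratory analysis. The wording of 9.1 would be met by a fall common to both arms, while the rest of the protocol asks for JITAI versus control. The only follow-up test named has no stated variable and adjusts for neither baseline nor the factor used to organise randomisation. On the stated change endpoint, its variance is 1.11 to 1.33 times that of ANCOVA, given SD 10 and a correlation of 0.8 to 0.5. At the upper end of that correlation range the gain is modest. The primary and secondary endpoints are untouched, and the planned t-test is imprecise rather than invalid.

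**What to change.** 1. **Section 9.1.** Restate the three exploratory hypotheses as JITAI minus control at Day 90. Report within-arm change descriptively only.
2. **Section 9.4.** For the HRQOL scores, replace the t-test with ANCOVA on the Day-90 score (arm, baseline score, condition) and report the adjusted difference with a 95% CI. If a nonparametric fallback is kept, name it. A repeated-measures model on Days 30, 60 and 90 is optional: it saves only about 2 to 6% of variance over ANCOVA but uses leavers who have a follow-up score. Choose one in advance.
3. **Missing scores.** Report the number per arm without a Day-90 score, counting replaced participants in the arm to which they were randomised.
4. **Sensitivity check.** Because baseline follows randomisation, show the unadjusted Day-90 difference beside the adjusted one. Its interval is wider (half-width 5.17 with 30 per arm).

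The cost is SAP wording and slightly more programming, with no extra data, visits or participants. If condition explains nothing, including it raises the standard error by about 0.5% at most, and by almost nothing if arms are balanced within condition. A fall in the JITAI arm alone could no longer be presented as support for the intervention.

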#### 9.4.2 ANALYSIS OF THE PRIMARY ENDPOINT(S)

##### Primary Endpoint:

- Feasibility & Acceptability Questionnaire: At the 3-month (90 day) assessment only, participants will complete a Study Feasibility survey to assess the experience of the participant with the study methodology and technology, including the CareQOL app, Fitbit®, and the JITAI. Items are scaled from 1 to 5 to indicate level of agreement, where "1" indicates "strong disagreement" and "5" indicates "strong agreement." Administration time is 5 minutes.

Frequency counts for each of the Feasibility and Acceptability items. Descriptive statistics will also be calculated.

#### 9.4.3 ANALYSIS OF THE SECONDARY ENDPOINT(S)

##### Secondary Endpoints:

- Attrition (% of participants completing the final assessment—the assessment that is given at the end of month 3)
- Adherence (% missing data of total expected data for each person)

Attrition will be reported as the number of participants that complete the final assessment out of the total of number of study participants that completed the baseline assessment. In addition, the total number of days that participants completed EMA assessments, the monthly surveys, and the number of participants that complete the study will be calculated. Descriptive statistics will be calculated for missing data across the study period and by moment/day.

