In this study, we will examine the acceptability and feasibility of a data collection protocol that involves the delivery of a personalized self-management intervention to promote care partner self-care. This just-in-time adaptive intervention (JITAI) is an emerging intervention that incorporates passive mobile sensor data feedback (sleep and activity [step] data from a Fitbit®), and real-time self-reporting of HRQOL via study specific app called CareQOL to provide personalized feedback via app alert. The proposed trial will examine the acceptability and feasibility of the JITAI in three distinct groups of care partners: 1) care partners for persons with a chronic condition that was caused by a traumatic event (i.e., spinal cord injury [SCI]); 2) care partners for persons with a progressive, fatal neurodegenerative disease (i.e., Huntington disease [HD]); and 3) care partners for persons with an episodic cancer condition that requires intense, prolonged inpatient and outpatient treatment (persons with hematopoietic cell transplantation [HCT]).

Participants in this study will be randomized either to a control group, where they will wear the Fitbit® and provide daily reports of HRQOL over a three-month (90 day) period (without the personalized feedback), or the JITAI group, where they will wear the Fitbit®, provide daily reports of HRQOL and receive personalized pushes for 3 months. 60-90 participants will be enrolled (n=20-30 care partners of persons with SCI; n=20-30 care partners of persons with HD; and n=20-30 care partners of persons with HCT). Half of the care partners of each condition will be randomized into the JITAI group and half of the care partners of each condition will be randomized in the control group.

We hypothesize that this intensive data collection protocol will be both feasible and acceptable for care partners, and that the intervention will have a positive impact on care partner mood (strain, depression and anxiety).

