## 4 STUDY DESIGN

### 4.1 OVERALL DESIGN

**Study Design:** This behavioral trial will use a two-arm randomized controlled design. Each of the 60-90 care partner participants will be randomized to an active “JITAI” arm (n=10-15 care partners of SCI, n=10-15 care partners of HD, n=10-15 care partners of HCT) or to a control arm (n=10-15 care partners of SCI, n=10-15 care partners of HD, n=10-15 care partners of HCT). The random allocation of participants to the treatment arm or control arm establishes the basis for testing the statistical significance or difference between the groups.

**Randomization:** Blocked randomization will be used to limit bias and achieve an equal distribution of participants to the control and treatment arms. A randomization list will be generated for each condition (SCI, HD, HCT) and the study statistician will oversee randomization. The participant will be randomized once he/she is deemed eligible and has provided informed consent (i.e. at enrollment prior to baseline data collection). The study coordinator/research assistant who consented the participant will use the appropriate condition’s randomization list to assign the participant to the correct study arm.

**Duration of Study Participation:** Study participation for both arms of the study (control and JITAI) involves a baseline assessment, followed by an approximate 10-day run-in period then a 3-month (90 day) home monitoring period (in which the intervention will be administered to the JITAI group). Thus, the total duration of the study is ~100 days.

**Study Sites:** This is a single-site study at the University of Michigan.

**Study Intervention:** The just in time adaptive intervention (JITAI) uses sensor data derived from the Fitbit® (e.g., accelerometer-based estimates of physical activity and sleep) and real-time self-report ratings (assessed once daily) of HRQOL (caregiver strain, depression, anxiety) to deliver personalized “pushes” to participants via a study specific app (CareQOL app). The personalized pushes will be delivered on ~50% of the days over the 3-month intervention period.

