### **8.1.2 CARE PARTNER ELIGIBILITY**

Confirmation of care partner eligibility according to criteria listed in Section 5, above, will be documented on the Eligibility CRF. It will occur prior to informed consent being obtained and before any study procedures associated with baseline assessment. Eligible individuals will then participate in the consent process, followed by randomization and baseline data collection.

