#### **8.1.5.1 BASELINE ASSESSMENTS**

Participants will be prompted by the CareQOL after registration to complete the baseline HRQOL assessments. Administration time is 10-15 minutes.

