#### Secondary Endpoints:

- 2) We hypothesize that this intensive data collection protocol will be both feasible and acceptable for care partners (regardless of group assignment)
  - a. Attrition as measured by the percent of participants completing the study (i.e., we expect  $\geq 80\%$  of participants to complete the study)
  - b. Percent missing data of total expected data for each person and on average will also be calculated to characterize the feasibility of this data collection method (i.e., we expect  $\leq 60\%$  missing data for the daily assessment questions and  $\geq 80\%$  completion rates for the three monthly surveys)

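### The retention formula in section 9.4.3 divides by baseline completers although randomisation comes first, so any randomised person without a completed baseline drops out and retention is biased upwards, by an amount the documents do not fix

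*Combined protocol and SAP*

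**What the plan says.** Section 9.1 (Secondary Endpoints) defines the endpoint as "Attrition as measured by the percent of participants completing the study" and expects at least 80%. It names no denominator. Section 9.3 gives the population: "Secondary endpoints will include attrition and adherence estimates (again across the full sample". Section 9.4.3 supplies the formula. Its numerator is the count of people who finish the month 3 assessment, and that count is taken "out of the total of number of study participants that completed the baseline assessment". Although it is called attrition, the quantity is a retention proportion.

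The order of events is stated twice and consistently. Section 4.1 randomises once eligibility and consent are in place, "i.e. at enrollment prior to baseline data collection". Section 8.1.2 says: "Eligible individuals will then participate in the consent process, followed by randomization and baseline data collection". Under section 8.1.5.1, part of baseline depends on the study app: "Participants will be prompted by the CareQOL after registration to complete the baseline HRQOL assessments".

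Three further rules bear on who counts. Section 6.2 terminates participants who cannot complete the run-in and notes them as screen failures. Section 7.1 replaces randomised people who do not finish the run-in, and also those who withdraw or are discontinued before the end of home monitoring. Section 5.4 defines screen failures as people who consent but are not then assigned to the intervention or entered in the study.

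**The concern.** Baseline completers are a natural denominator when baseline comes before randomisation. Here it comes after. Someone who is consented and randomised but does not register the app, or stops during the opening questionnaires, has been enrolled and then lost, yet is counted neither as a completer nor as a loss.

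This matters because feasibility is the purpose of the trial. The primary questionnaire is given only at day 90, so it cannot capture people who left at the start. The retention proportion is the measure that could, and the formula as written leaves out the earliest losses. The error runs in one direction only, towards meeting the 80% expectation.

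**Working it through.** **Inputs.** Planned enrolment: "60-90 participants will be enrolled" (section 1.1); section 9.2 argues from N = 60. Benchmark: at least 80% (section 9.1). This is an expectation with no derivation, and section 9.2 reports no formal power calculation, so there is no plan figure to reproduce. The number randomised without a completed baseline, m, is not given; the values of m below are assumptions.

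**Formulas.** Let N be all randomised, B = N − m the baseline completers and C the final-assessment completers.

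- Section 9.4.3 reports C/B. Retention among all randomised is C/N.
- C/B = (C/N) × (N/B). Since N/B is at least 1, the reported figure is never below C/N, and it exceeds C/N as soon as m is 1 or more (for C above 0).
- The pass mark under section 9.4.3 is the smallest whole C with C/B at or above 0.80. With all randomised it is 48 of 60 or 72 of 90.

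**Pass marks under section 9.4.3.**

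| N | m (assumed) | B | Completers needed | C/B | C/N |
|---|---|---|---|---|---|
| 60 | 0 | 60 | 48 | 80.0% | 80.0% |
| 60 | 1 | 59 | 48 | 81.4% | 80.0% |
| 60 | 2 | 58 | 47 | 81.0% | 78.3% |
| 60 | 3 | 57 | 46 | 80.7% | 76.7% |
| 60 | 6 | 54 | 44 | 81.5% | 73.3% |
| 90 | 4 | 86 | 69 | 80.2% | 76.7% |
| 90 | 9 | 81 | 65 | 80.2% | 72.2% |

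With one loss in 60 the pass mark does not move. With three it falls by two completers.

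**Chance of observing at least 80%.** These are binomial tails with m fixed, N = 60, m = 3 and a true completion rate p among all randomised (assumed). The rate among baseline completers is then p × 60/57.

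| p | Denominator B (need 46 of 57) | Denominator N (need 48 of 60) |
|---|---|---|
| 65% | 0.028 | 0.009 |
| 76% | 0.527 | 0.289 |
| 85% | 0.986 | 0.894 |

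The 76% row is close to the most sensitive case: 0.76 × 60/57 = 0.80, so the rate among baseline completers sits exactly on the threshold. Away from it the two denominators differ less. With m = 1 and p = 76% the chances are 0.284 and 0.289, in effect equal.

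**Run-in failures and replaced participants.** These losses come after baseline, so a literal reading of section 9.4.3 keeps them in B. But sections 5.4 and 6.2 label run-in failures as screen failures and section 7.1 replaces them. Whether they remain study participants for this formula is not stated. If they were also removed, the same arithmetic applies with a larger m. For example, 3 without baseline plus 3 run-in failures (assumed) gives m = 6, the fifth row of the first table.

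**The case against.** The strongest reply is that very few people can be lost in this gap. The schedule in section 1.3 puts consent, randomisation, baseline surveys and app instructions on one enrolment day. Section 6.2 has staff help each participant download and register both apps at the baseline visit. Section 5.1 requires a device, internet access, and the willingness and ability to complete all assessments, and section 8.1.2 checks this before consent. Technology troubleshooting belongs to the run-in, after baseline. All of this stands, and it limits the likely size. A reader might infer that the formula hides most technology failures; the documents do not support that, because many of them should surface in the run-in.

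A second reply is that there is no true contradiction. Section 9.1 names no denominator, and section 9.3 never defines the full sample as all randomised: it may only mean pooling the arms, and section 9.3 ties intention-to-treat to the exploratory analyses alone. This also stands. A reader might take section 9.4.3 to break a stated all-randomised population; the text shows only that the wordings fit poorly together.

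A third reply is that this is a descriptive secondary endpoint in a pilot, with an expectation and no decision rule. That lowers the consequence but does not justify a denominator that can only flatter the result. Section 9.4.3 also reports how many complete the study, but as a count with no denominator.

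**Conclusion.** The concern holds as a one-directional bias of unknown and possibly small size. It rests on the explicit denominator in section 9.4.3 and on the order of randomisation and baseline in sections 4.1 and 8.1.2, neither of which is contradicted elsewhere.

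The magnitude depends entirely on an assumed number lost between randomisation and completed baseline. Three lost of 60 would let a true 76.7% be reported as 80.7%; one or none would leave the pass mark where it is. A reader might take 0.53 against 0.29 as the expected effect on the chance of meeting 80%. It is not: it needs three losses and a completion rate placed on the threshold, and the documents give neither.

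It is equally tempting to treat the standing of run-in failures as settled, in either direction. It is not settled, so changing the denominator phrase alone would leave the figure open to more than one reading. The same holds for what counts as a completed baseline: section 9.4.3 does not define it, and only the HRQOL battery is expressly prompted by the app.

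**What to change.** In section 9.4.3:

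- Make all randomised participants the denominator for the 80% criterion.
- State that randomised participants stay in it as non-completers if they do not complete baseline, are noted as screen failures in the run-in (section 6.2), or withdraw and are replaced (section 7.1).
- State that replacements enter as further randomised participants and do not take over the place of those they replace.
- Keep the baseline-completer percentage as a supplementary figure, with a sentence defining a completed baseline.
- Show the number randomised without a completed baseline as a line in the participant flow.

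Using the same term in section 9.3 would remove the doubt about the full sample. The cost is a few sentences and one line in the flow; the counts can be taken from the randomisation lists described in section 4.1. The one small downside is that reported retention may be slightly lower.
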